Number of subjects planned	Up to 24 patients in 3 idronoxil dose level cohorts of 4 patients (n=12) and an expansion cohort of 12 patients.
Indication / Patient Population	Metastatic castrate-resistant prostate cancer with no remaining standard treatment options. Patients must have at least one metastatic lesion which is amenable to RT.
Study period and duration of treatment	The study will comprise two parts: 1. Treatment and follow up (24 weeks) comprising: 
• NOX66 (Day 1-16)• Palliative Dose Radiation therapy (Day 2-9)• 6-week follow up• 12-week follow up• 24-week follow up 2. Long term follow-up: 
• Ongoing follow up and monitoring of patient to assess long term effects of NOX66 administration and survival including scheduled follow up at 9, 12, 15, 18, 21 & 24 months from treatment commencement date.
Primary study objective	
• To determine the tolerability and toxicity of NOX66 administered in conjunction with palliative radiation therapy
Secondary study objectives	
• To observe any clinical response to treatment of NOX66 in combination with palliative radiation therapy• To observe the effects of NOX66 use on long term (24 months) outcomes for patients

	
 • To document Progression Free Survival (PFS) and Overall Survival (OS) of patients • Exploratory: to measure levels of idronoxil

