8.3 EXCLUSION CRITERIA

Patients who have any of the following exclusion criteria are not eligible to participate in the study:

1. Tumour involvement of the central nervous system
2. Uncontrolled infection or systemic disease

3. Clinically significant cardiac disease not well controlled with medication (e.g. congestive heart failure, symptomatic coronary artery disease, angina, and cardiac arrhythmias) or myocardial infarction within the last 12 months
 - Patients with a QTc > 470 msec on screening ECG
4. Concurrent systemic chemotherapy or biological therapy
5. Any situation where the use of suppository therapy is contra-indicated or impractical (eg. chronic diarrhoea, colostomy, ulcerative colitis).
6. Known human immunodeficiency virus (HIV) or Hepatitis B or C (active, previously treated or both)
7. Any subject whose testosterone is not suppressed i.e. is > 0.5nmols/L.
8. Any other reason which, in the opinion of the investigator, will preclude suitable participation in the study.

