9.6 CONCOMITANT MEDICATIONS

Patients are permitted a wide range of medications for general health, although this is to be confirmed with the Sponsor prior to enrolment into the Study.

Patients are permitted certain medications specifically related to their metastatic disease, including use of androgen deprivation therapy (ADT) such as luteinizing hormone-releasing hormone (LHRH) agonists and antagonists. Other therapies are to be confirmed with the Sponsor medical monitor prior to enrolment in the Study.

Patients are not permitted any other experimental treatments. Supportive care measures and treatment for symptom control are permitted, including analgesics. Treatment of constipation or diarrhea is permitted however the investigator must determine the suitability of these patients to continue taking suppositories should these adverse events (as scored by NCI CTCAEv4.03) be reported. Patients will be medically monitored so that any adverse events will be identified promptly and treated appropriately.

Details regarding the name, indication, route of administration, dose, and frequency of all medications taken within 14 days prior to study drug administration will be recorded in the eCRF at the Screening Visit and Day 1. Details regarding the name, indication, route of administration, dose, and frequency of all medications taken during the study will be recorded in the eCRF at each patient visit. "All medications" should include prescription, over-the-counter (OTC) medications, dietary/nutritional supplements, and herbal products.

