10.2.6 Eighteen -Week administration BPI-SF (Day 125 ± 5)

The Brief Pain Inventory- Short Form questionnaire will be verbally administered to patients by site staff via the telephone. Site staff will schedule a suitable time with the patient to conduct the phone interview and document patient responses.

10.2.7 Twenty-Four Weeks Follow up/ end of study (Day 168 ±7) -VISIT 10

Visit 10 will occur 154 days/22 weeks post completion of NOX66 treatment and consist of the following assessments:

- Physical Examination including vital signs
- Performance Status Assessment (using ECOG performance scale)
- Electrocardiography in triplicate
- Safety blood sampling - Complete Blood Count, Serum Chemistry and Urinalysis
- Biomarker blood sampling – PSA
- Administration of Brief Pain Inventory -Short Form questionnaire
- Concomitant Medication Review
- Adverse Event Review (CTCAE 4.03)
- Tumour Imaging (CT/MRI scan) and Assessment

All patients currently in the study or follow up period, will be asked to re-consent with the revised ICF in order to agree to participate for additional follow up visits (Visit 11 to 16).

For patients who have withdrawn from the study prior to study completion or completed End of Study visit (Visit 10) at the time of this amendment implementation, the investigator or designee will make contact by phone to seek patient willingness to participate in long term follow up and if the patient agrees, a visit will be scheduled for reconsenting.

For Patients who have completed End of Study Visit (Visit 10) at 24 weeks and are unable to be contacted or are > 6 months post EOS, the Investigator or designee at each study site will review medical records from End of Study visit to most recent information available and report on:

- Disease status based on available radiology or other assessments
- Patient Survival information
- Any new anti-cancer treatment after discontinuation of study treatment

10.2.8 Month 9 Long Term Follow up -Visit 11

Visit 11 will occur approximately 3 months after 24 weeks follow up (Visit 10) and consist of the following assessments:

- Performance Status Assessment (using ECOG performance scale)
- Biomarker blood sampling – PSA
- Administration of Brief Pain Inventory -Short Form questionnaire
- Tumour Imaging (CT/MRI/US scan) and Assessment
- Report of any pain medication and any anti-cancer treatment after discontinuation of study treatment

10.2.9 Month 12 Long Term Follow up -Visit 12

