Visit 12 will occur approximately 6 months after 24 weeks follow up (Visit 10) and consist of the following assessments:

- Performance Status Assessment (using ECOG performance scale)

- Biomarker blood sampling – PSA
- Administration of Brief Pain Inventory -Short Form questionnaire
- Tumour Imaging (CT/MRI/US scan) and Assessment
- Report of any pain medication and any anti-cancer treatment after discontinuation of study treatment

10.2.10 Month 15 Long Term Follow up -Visit 13

Visit 13 will occur approximately 3 months after the previous visit and consist of the following assessments:

- Biomarker blood sampling – PSA
- Tumour Imaging (CT/MRI/US scan) and Assessment
- Report of any pain medication and any anti-cancer treatment after discontinuation of study treatment

10.2.11 Month 18 Long Term Follow up -Visit 14

Visit 14 will occur approximately 3 months after the previous visit and consist of the following assessments:

- Biomarker blood sampling – PSA
- Tumour Imaging (CT/MRI/US scan) and Assessment
- Report of any pain medication and any anti-cancer treatment after discontinuation of study treatment

10.2.12 Month 21 Long Term Follow up – Visit 15

Visit 15 will occur approximately 3 months after the previous visit and consist of the following assessments:

- Biomarker blood sampling – PSA
- Tumour Imaging (CT/MRI/US scan) and Assessment
- Report of any pain medication and any anti-cancer treatment after discontinuation of study treatment

10.2.13 Month 24 Long Term Follow up -Visit 16

Visit 16 will occur approximately 3 months after the previous visit and consist of the following assessments:

- Biomarker blood sampling – PSA
- Tumour Imaging (CT/MRI/US scan) and Assessment

- Report of any pain medication and any anti-cancer treatment after discontinuation of study treatment

Patients who have disease progression during any of the follow up periods between Visit 10 and Visit 16, will be followed up for survival information by the Investigator or designee via a telephone contact.

All data collected from Visit 11 to 16 will be entered in a paper CRF provided by the Sponsor or delegate.

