12 STATISTICAL SECTION

12.1 SAMPLE SIZE

The study is intended as a Proof of Concept and dose confirmation study, providing justification for and guidance on the design of further studies.

The primary objective of this study is to observe safety and tolerability of idronoxil (NOX66) in combination with radiation therapy (at palliative doses). In conjunction with observations

from the other phase 1 trials in the NOX66 development program, 24 patients are considered adequate to inform on toxicity and safety in order to progress to phase 2/3.

Palliative Radiation therapy alone is unlikely to provide more than a minor and temporary reduction (<30%) in tumour size. Any responses greater than this will be considered to be related to NOX66 use. Any signals of efficacy will be described in the Clinical Study Report and used to support the Phase 2/3 development program.

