12.2 STATISTICAL METHODOLOGY

This section describes the planned statistical analyses in general terms. A complete description of the statistical analysis will be specified in a statistical Analysis Plan (SAP) finalised prior to completion of the study.

General: Data will be summarized by using counts and percents for discrete parameters, and by descriptive statistics (e.g. number of observations, mean, standard deviation, median, minimum and maximum) for continuous parameters. Subject disposition and baseline characteristics will be presented for all treated patients. Data will be analysed as collected. No imputation of values for missing data will be performed. Standard clinical monitoring and data management practices will be used to ensure the integrity of the data.

Populations for analysis: There will be two study populations defined for this study. The safety population will consist of all patients who received at least one dose of NOX66. This population will be used in all safety summaries. The efficacy population will consist of all patients who complete radiation therapy with at least 7 days of NOX66 dosing.

Baseline Comparisons and Patient Disposition: Demographic and baseline disease characteristic data summarisation will be performed in order to descriptively document any safety and efficacy findings. Data to be tabulated will include demographic features such as age and race, as well as medical history. The number and percentage of patients who complete the study or who withdraw for any reason will be presented.

Efficacy Analysis: Results from (i) RECIST 1.1 response assessment for target lesions and non-target lesions, (ii) ECOG Performance Score and (iii) Pain scores. Changes from baseline in levels of serum PSA levels will be listed.

Overall and progression-free survival, PSA and pain scores collected during the extended follow-up period will be summarized in the same manner as for the immediate post-treatment follow-up period.

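### Standard anti-cancer therapy after the NOX66 course is not barred and is recorded, but PFS has no rule for it and section 12.1 would credit a later agent's tumour response to NOX66

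*Combined protocol and SAP*

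**What the plan says.** **Treatment and follow-up.** Section 10.2.3 gives NOX66 for 13 to 16 days. Section 7 sets assessments at Weeks 6, 12 and 24 and then every 3 months to month 24.

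**Other therapy.** The one prohibition in section 9.6 is "Patients are not permitted any other experimental treatments". Exclusion 4 in section 8.3, "Concurrent systemic chemotherapy or biological therapy", is an entry criterion. Section 9.6 also wants other disease-related therapies agreed with the medical monitor, but before enrolment.

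**What is recorded.** Section 10.2.7 lists, for the review of medical records, "Any new anti-cancer treatment after discontinuation of study treatment". Sections 10.2.8 to 10.2.13 (Visits 11 to 16) each list "Report of any pain medication and any anti-cancer treatment after discontinuation of study treatment".

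**What is analysed.** Section 12.2 says "Data will be analysed as collected" and, on the long-term data, "Overall and progression-free survival, PSA and pain scores collected during the extended follow-up period will be summarized in the same manner as for" the first follow-up period. It also has concomitant medications listed for every patient. Section 10.1 defines PFS only as a duration counted from the start of study treatment. On tumour shrinkage past what radiotherapy alone is expected to give (less than 30%), section 12.1 says "Any responses greater than this will be considered to be related to NOX66 use".

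**Population.** The synopsis describes "Metastatic castrate-resistant prostate cancer with no remaining standard treatment options". None of the 12 criteria in section 8.2 asks for this.

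**The concern.** A new anti-cancer agent started during follow-up is an intercurrent event for every efficacy outcome except, by usual choice, OS. The plan expects it, since it asks sites to report it, but gives it no role in the efficacy analysis.

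Take a patient who starts a new agent in Week 10 and has at least 30% shrinkage at Week 24. Read literally, section 12.1 makes that a NOX66 response. If no progression was recorded before the switch, PFS also runs on under the new agent.

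There is no control arm in which the same thing would happen, so an effective later agent moves the results in NOX66's favour. Sections 7 and 12.1 intend these results to support a Phase 2/3 programme, and a synopsis objective concerns the effect of NOX66 on 24-month outcomes.

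**Working it through.** The plan states no figure to reproduce here: no alpha, power, target effect or rate of later therapy. The check is mainly a reading of sections against each other.

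**1. Can new therapy overlap with efficacy readings?** Yes. No section forbids standard therapy after the course, though none expressly grants it either. From Visit 11 it is reported at the same visits as PSA and scans. Section 8.4 keeps withdrawn patients in follow-up unless they withdraw consent.

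**2. Does any efficacy rule use the information?** None found. Section 10.1 gives no PFS censoring rule, and section 12.2 has no cut-off or sensitivity analysis. The inputs that section 10.4.9 names for the expert committee are scans, PSA, ECOG and pain, not later therapy.

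**3. Which outcomes are exposed?**

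| Outcome | Exposure | What limits it |
|---|---|---|
| Tumour response | Week 12 onward; explicit attribution in 12.1 | Week 6 leaves least time for a new agent |
| PFS | Therapy started before progression is recorded | If progression is recorded first, the event has already occurred |
| PSA | Therapy started before Week 24, or later without recorded progression | Progression between Visits 10 and 16 leads to telephone survival follow-up (10.2.13) |
| Pain | As PSA, but only to Month 12 | BPI-SF is not scheduled after Visit 12; the Week 12 response has an opiate condition (10.4.5), which does not cover anti-cancer therapy |
| OS | Reported regardless of later therapy | Usual choice; no change needed |

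**4. Could the analyst separate the values afterwards?** Not reliably. Section 9.6 lists the medication details to record at each visit, and a start date is not among them. The Visit 11 to 16 lists do not ask for one either.

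**5. Scale.** Days from the last possible dose (Day 16) to each reading:
- Week 6: 43 − 16 = 27
- Week 12: 84 − 16 = 68
- Week 24: 168 − 16 = 152

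These show the opportunity to start another agent. They do not measure bias.

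Weight of one responder whose response follows a new agent:
- all patients: 1/24 = 4.2 points
- expansion cohort: 1/12 = 8.3 points

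RECIST target-lesion response applies only to patients with measurable lesions, so its denominator may be smaller and the weight larger.

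For illustration only, let f be the share of 24 patients who start new therapy while still assessed and q the share of those who respond to it. Neither is in the documents. Expected misattributed responders = 24 × f × q, and the chance of at least one = 1 − (1 − fq)^24.

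| f | q | Expected responders | Points | Chance of at least one |
|---|---|---|---|---|
| 10% | 10% | 0.24 | 1.0 | 21% |
| 25% | 30% | 1.8 | 7.5 | 85% |
| 50% | 50% | 6.0 | 25.0 | over 99% |

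The range is too wide to serve as an estimate.

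**The case against.** The strongest reply is that section 12.2 speaks in general terms and leaves the detail to a full SAP, where censoring rules usually sit. The statement about analysing data as collected stands beside the no-imputation rule and may be meant only for missing data. That is fair as far as it goes. But no such rule is in the text available, and the attribution in section 12.1 is a positive statement with no exception, so the point is more than missing detail.

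Second, later therapy is not ignored: medications are reviewed at Visits 8 to 10 and listed for all patients, and the synopsis plans per-patient tables. In 24 patients a careful reader could set therapy beside response. This stands in part, but without start dates the order of events may not be recoverable.

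Third, patients who progress between Visits 10 and 16 move to survival follow-up, and the expansion dose is chosen on Week 6 data, when exposure is least. Both stand and narrow the point.

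Fourth, describing outcomes regardless of later therapy is legitimate, and censoring PFS at a switch can be informative when deterioration prompts the switch. This also stands, and is why both PFS presentations are needed.

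Fifth, the synopsis population suggests few options remain. That may lower uptake, but section 8.2 does not enforce it.

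**Conclusion.** The concern holds in a limited form. As written, a tumour response at Week 12 or later that follows a new agent would be credited to NOX66. PSA and, to Month 12, pain may carry the new agent's effect in patients who start it before Week 24 or without recorded progression. PFS may do so where the switch comes before recorded progression.

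A reader might infer that PSA, pain, tumour response and PFS are all equally contaminated through month 24 and all expressly credited to NOX66. The documents do not support that. The explicit crediting covers tumour size only; for the other outcomes it is an inference from the objectives and the absence of a rule. Pain collection ends at Month 12, and patients progressing after Visit 10 are largely protected. Nor can a bias of a given number of points be claimed, or one be read from the short share of follow-up spent on treatment, because response to a short course is always assessed after it ends.

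The size is therefore unknown beyond 4.2 points per affected responder in 24, or 8.3 in 12. The conclusion assumes that some patients start effective therapy while still assessed, that telephone follow-up replaces scheduled PSA, pain and scans after progression, and that the later SAP adds no rule. The primary safety objective is unaffected.

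**What to change.** - **Section 12.2, response.** Summarise RECIST, PSA and pain response from assessments made before the first new anti-cancer therapy. List and flag later values.
- **Section 12.2, PFS.** Present it twice: as collected, and censored at the last tumour assessment before new therapy. State that this censoring may be informative.
- **OS.** Leave uncensored.
- **Data collection.** Record the start date of each new anti-cancer therapy from Visit 8 onward.
- **Section 12.1.** Limit the attribution to responses seen before any new anti-cancer therapy.
- **Separately.** The synopsis population and the criteria in section 8.2 must be reconciled; this is an eligibility matter apart from the analysis.

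The cost is wording in sections 12.1 and 12.2 and the SAP, plus a date field in the eCRF and in the paper form used for Visits 11 to 16. The downside is fewer evaluable late values and possibly informative censoring in one of the two PFS presentations.

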8.4 SCREEN FAILURE AND STUDY WITHDRAWAL

Patients should begin protocol treatment within 2 weeks of enrolment at screening. Issues that would cause treatment delays longer than 2 weeks should be discussed with the Sponsor. If a patient does not proceed to receive protocol therapy following enrolment at screening, the patient's study enrolment will be cancelled, and the patient will be considered a screen failure. The Sponsor should be notified of screen failures as soon as possible.

Patients will be informed that they are free to withdraw from the study at any time and for any reason. Withdrawal criteria, other than progressive disease, can be defined as one or more of the following:

- an inter-concurrent illness that prevents further administration of idronoxil (NOX66) or radiation therapy;
- an adverse event to the combination treatment that is intolerable;
- the patient withdraws consent;
- the patient dies;
- general or specific changes in the patient's condition render the patient unacceptable for further treatment in the judgment of the Investigator.

In all cases, the reason for withdrawal must be recorded in the CRF and in the patient's medical records. The patient must be followed to establish whether the reason was an adverse event causally related to idronoxil (NOX66), and, if so, this must be reported in accordance with the requirements for adverse event reporting.

Patients will continue to be followed for the duration of the study, unless consent is withdrawn.

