10.2 STUDY VISITS

The total study duration per patient will be a minimum of 25 weeks, with continued follow up up to 24 months from the treatment commencement date:

- Screening period: to occur within 2 weeks prior to the scheduled date of treatment commencing
- Treatment and follow up period: up to 24 weeks from the commencement of the first dose of NOX66 and it includes enrolment visit to occur prior to Day 1 of treatment
Long term follow up visits: every 3 months from week 24 for another 18 months.
Observation period (post study follow-up visits): Continued observation of patients beyond 24 months follow up visit, at the discretion of the investigator.

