Safety Analysis: The safety will be assessed through the analysis of the reported incidence of treatment emergent AEs, including SAEs, dose-limiting toxicities, AEs leading to withdrawal, events of at least CTCAE Version 4.03 Grade 3 in severity, and AEs related to study treatment. Treatment emergent AEs are those with an onset on or after the initiation of therapy. Other safety endpoints include laboratory results, physical examinations, vital signs, and changes in ECOG status. A copy of CTCAE Version 4.03 scoring system may be downloaded from:

http://evs.nci.nih.gov/ftp1/CTCAE/CTCAE_4.03_2010-06-14_QuickReference_8.5x11.pdf.

The adverse events will be summarized by MedDRA coding terms, System Organ Class (SOC), and preferred term for all treated patients and by dose cohort. The AEs will also be tabulated by maximum severity and maximum relationship to study drug where applicable. The number and percent of patients experiencing dose-limiting toxicities will be summarized by dose cohort, by DLT, and system organ class for all treated patients. Other safety endpoints, which include change from baseline in laboratory results and vital signs, and shifts in physical examinations, will be summarized throughout the study by visit for each dose level for all treated patients.

Concomitant medications: are to be listed for all patients.

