14 ADVERSE EVENTS REPORTING

Adverse events (AE) or serious adverse events (SAE) reported by the patient or observed by the Investigator will be listed individually on an adverse event form in the CRF. The signs and symptoms, time of onset, duration, treatment (if any), and follow-up procedures (if any) will be reported, and the criteria for assessing causality to study drug and outcome categories should be defined.

Pre-existing conditions or illnesses which are expected to exacerbate or worsen are not considered adverse events and will be accounted for in the patient's medical history.

All adverse events are to be followed up for 30 days following the end of study or until resolution (whichever is sooner).

In order to classify AEs and diseases, preferred terms will be assigned by the Sponsor to the original terms entered on the eCRF using the Medical Dictionary for Regulatory Activities (MedDRA).

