14.1 DEFINITIONS

14.1.1 AE

AE is any un-anticipated or unintended medical occurrence or worsening of a sign or symptom (including an abnormal laboratory finding) or disease in a study participant, which does not necessarily have a causal relationship with the study condition, procedures or study agent(s) that occurs after the informed consent is obtained.

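### Section 12.2 defines treatment-emergent AEs by onset alone, so a pre-dose AE that worsens on treatment can drop out of the treatment-emergent outputs, depending on how it was recorded

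*Combined protocol and SAP*

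**What the plan says.** The safety paragraph of section 12.2 sets the frame: "The safety will be assessed through the analysis of the reported incidence of treatment emergent AEs, including SAEs, dose-limiting toxicities, AEs leading to withdrawal". The same sentence goes on to events of Grade 3 or higher and to related AEs. It then gives the only definition of treatment emergence in the document: "Treatment emergent AEs are those with an onset on or after the initiation of therapy". Further on, it says: "The AEs will also be tabulated by maximum severity and maximum relationship to study drug where applicable".

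Section 14.1.1 defines an AE as including "worsening of a sign or symptom (including an abnormal laboratory finding) or disease in a study participant", and limits it in time to one "that occurs after the informed consent is obtained". Section 14 has each event listed individually in the CRF: "The signs and symptoms, time of onset, duration, treatment (if any), and follow-up procedures (if any) will be reported".

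On the time between consent and dosing, section 10.2 says "Screening period: to occur within 2 weeks prior to the scheduled date of treatment commencing". Section 8.4 says "Patients should begin protocol treatment within 2 weeks of enrolment at screening" and asks that longer delays be discussed with the sponsor.

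No section says whether a rise in grade opens a new AE record or updates the existing one.

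**The concern.** AEs are collected over a window that opens before treatment, but treatment emergence is decided by onset date only. Suppose a patient develops Grade 1 fatigue or nausea after consent and before Day 1, and it reaches Grade 3 during NOX66 and radiotherapy. The event has been collected. If it carries its pre-dose onset date, the rule in 12.2 then removes it from the treatment-emergent outputs, although the severe phase happened on treatment.

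Safety and tolerance form the primary objective (section 6.1), and 12.2 frames the safety assessment around treatment-emergent AEs. The cohorts are small, so one patient counted or not counted is visible in any percentage by dose. The study also runs at sites in three countries (section 3.3). Without a recording rule, two sites could enter the same course of toxicity differently and both comply with the protocol.

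**Working it through.** There is no figure in the plan to reproduce, because the point is one of definition. The check has three steps.

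**1. Does a pre-dose window exist?** Yes. AEs count from consent (14.1.1). Screening falls within 2 weeks before treatment (10.2), and 8.4 allows for longer delays. The window is narrow in practice. Significant abnormalities found at the screening examination go to medical history (10.4.2), and the first AE review in Table 1 is on Day 2. Only events that first arise between consent and first dose are affected.

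**2. What does the rule do with an event that starts in that window and reaches Grade 3 on treatment?**

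| Way of recording | Onset on record | Treatment emergent under 12.2? |
|---|---|---|
| One record, grade updated | Before Day 1 | No |
| New record at the grade rise | After Day 1 | Yes |

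Text that fits the first row:
- Section 14 asks for the time of onset and duration of each listed event.
- Section 12.2 tabulates by maximum severity, which suits a record whose grade changes. It also suits the worst grade per patient across several records.
- Section 14.2.1 speaks of non-serious AEs becoming serious, so it treats an escalating event as the same event. That concerns seriousness, not grade.

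Text that fits the second row:
- Section 14.1.1 makes worsening an AE in itself.
- Sections 10.4.2 and 10.4.4 have follow-up changes on examination and ECG reported as AEs.

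Neither set of passages settles the matter.

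**3. How large is the effect of one omitted patient?** The inputs are the planned sizes in the synopsis: three cohorts of 4 plus an expansion cohort of 12, so 3 × 4 + 12 = 24. The shift in an incidence is 100/n percentage points.

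- Dose cohort of 4: 100/4 = 25.0 points.
- Dose group of 16 (4 + 12, assuming that the expansion uses a dose given to exactly one earlier cohort): 100/16 = 6.25 points.
- All 24: 100/24 = 4.2 points.

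The documents give no frequency for such events. For illustration only, let q be the assumed share of patients with an event that starts before dosing, worsens on treatment and is kept as one record. The chance of at least one such patient is 1 − (1 − q)^n.

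| q (assumed) | n = 4 | n = 24 |
|---|---|---|
| 1% | 3.9% | 21.4% |
| 2% | 7.8% | 38.4% |
| 5% | 18.5% | 70.8% |
| 10% | 34.4% | 92.0% |

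These values show how the chance depends on q. They are not an estimate for this trial.

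**The case against.** The strongest reply is that 14.1.1 already deals with this. If worsening is itself an AE, a rise to Grade 3 on treatment is a new event with on-treatment onset, and 12.2 counts it. That reading is legitimate, so loss of the event is possible but not certain. It does not close the gap, because nothing tells sites to record in that way and other passages fit a single continuing record.

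A second reply is that section 12.2 is written in general terms and leaves full detail to a SAP. That is true. But 12.2 states a specific rule here, which a SAP would naturally carry forward, so this is more than a missing detail.

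A reader might go further and infer that the primary safety result is biased downwards, or that such events vanish from every safety table. The documents do not support either inference:
- The primary outcome measures in 10.1, including the count of events above Grade 2, are not limited to treatment-emergent AEs. Nor is the primary endpoint in the synopsis.
- In 12.2, the summary by system organ class and preferred term and the separate DLT table are worded for all treated patients.
- The synopsis has adverse events listed per patient, and laboratory changes from baseline are summarised by visit.

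A reader might also infer that dose escalation is affected. Section 10.2.14 escalates on discontinuations due to NOX66-related events, and section 13.2 sends related events of Grade 2 and above to the steering committee directly. Neither uses the treatment-emergent definition.

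**Conclusion.** The concern holds in a limited form. The rule in 12.2 lacks a worsening clause and the protocol lacks a rule for recording grade changes. Whether a pre-dose AE that worsens on treatment enters the treatment-emergent outputs therefore depends on how the site recorded it. A related consequence is that the same Grade 3 event can be in the 10.1 count of events above Grade 2 and absent from the 12.2 summary of treatment-emergent events of Grade 3 or higher.

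Each omitted patient is worth 25 points in a cohort of 4 and 4.2 points among 24. How many would be omitted cannot be said from the documents. The conclusion rests on two conditions: that an event arises between consent and first dose, and that it is kept as one record with its first onset date. The separate exclusion in section 14 of pre-existing conditions expected to worsen is not part of this point. The correction should be made before the SAP is finalised.

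**What to change.** Replace the definition in section 12.2, and carry it into the SAP, with: *Treatment-emergent AEs are those with onset, or an increase in CTCAE grade over the highest grade between consent and first dose, on or after the first dose of NOX66.* Naming the first NOX66 dose also matches the safety population in 12.2.

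State in section 14 and the CRF instructions that a grade increase is recorded with its date, either as a new record or as a dated grade change on the existing one. Choose one method for all sites and make it consistent with the AE definition in 14.1.1.

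The cost is one sentence and one CRF date field. Reported treatment-emergent counts may rise slightly. No dosing, escalation or other clinical rule changes.
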